13.2.2.1 Demographic and Other Baseline Characteristics

Demographics and baseline characteristics will be presented using summary statistics for each treatment group and in total.

13.2.3 Hypotheses and Statistical Methods

13.2.3.1 Analysis of Primary Endpoint Variable

The primary efficacy variable will be change in log-transformed C-peptide AUC_{mean 0-120 min} during an MMTT from baseline to Month 15. Mean changes from baseline will be analyzed using Mixed Model Repeated Measures (MMRM). The model for analysis will include fixed, categorical effects of treatment, randomization

strata (GAD65A level), visit and treatment by visit interaction, as well as the continuous, fixed covariates of log-transformed baseline C-peptide $AUC_{\text{mean } 0-120}$ during an MMTT. An unstructured (co)variance structure will be used to model the within-patient errors. If this analysis fails to converge, compound symmetry will be tested. The (co)variance structure converging to the best fit, as determined by Akaike's information criterion will be used as the primary analysis. The Kenward-Roger approximation will be used to estimate denominator degrees of freedom. The primary treatment comparison will be the contrast between treatments at Month 15 for active treatments versus placebo.

Least Square (LS) Mean estimates and 95% confidence intervals (CIs) will be back-transformed from the log scale to the original scale and given together with nominal p-values. Back-transformed estimates of the treatment difference will provide an estimate of the (Diamyd/placebo)-ratio in the relative change from baseline in AUC. Here a ratio of e.g. 0.8 will mean that the change from baseline to month 15 in C-peptide level was 20% smaller for Diamyd than for placebo at Month 15.

A sensitivity analysis where the hypotheses will also be assessed using Analysis of Covariance (ANCOVA) adjusted for baseline value of C-peptide ($AUC_{\text{mean } 0-120 \text{ min}}$) during an MMTT between baseline to 15 months and randomization strata (GAD65A level) using the completers set.

Further sensitivity analyses will be given in the SAP.

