
Endpoints:
 
Primary Endpoint:
 
 Change in C-peptide (Area Under the Curve [AUC]_{mean 0-120 min}) during a Mixed Meal Tolerance Test (MMTT) between baseline to 15 months. 
Key Secondary Endpoints:
 
 Change in insulin-dose-adjusted HbA1c (IDAA1c) between baseline and 15 months Change in Hemoglobin A1c (HbA1c) between baseline and 15 months Change in daily exogenous insulin consumption between baseline and 15 months. 
Secondary endpoints:
 
 Other variables that indicate Diabetes Status such as plasma C-peptide, variability of blood sugar, and number of self-reported hypoglycemia. Variables that indicate treatment safety such as occurrence of adverse events (AEs), physical examinations, hematology, urine analysis, injection site reactions, GAD65A titer, vital signs and clinical chemistry. Variables that indicate effects on the immune system such as serum autoantibodies (and isotypes) to GAD65, serum cytokine levels, secretion of cytokines by immune cells in response to GAD65-stimulation, and proportions of immune cells in blood. Measurements of patient QoL by questionnaire. 
Exploratory Endpoints:
 
 All data collected at the 24-month follow-up visit will be regarded as exploratory endpoints. 
Sample size:
 
A total sample size of 106 patients is planned for a 1:1 randomization in order to provide 90% power to detect a 50% difference in geometric mean C-peptide (AUC_{mean 0-120 min}) at 15 months between the active arm and placebo arm using a two-sided test at the 0.05 level, with 10% loss to follow-up. This is based upon a t-test employing ln(X+1) normalizing transformation of C-peptide (AUC_{mean 0-120 min}) during an MMTT at 15 months and assumed mean and standard deviation estimates, on the transformed scale, of 0.134 and 0.20 respectively.
 
Analysis of Primary endpoint variable:
 
The mean change in log-transformed values will be analyzed using Mixed Model Repeated Measures (MMRM). The model for analysis will include fixed, categorical effects of treatment, randomization strata (GAD65A level), visit and treatment by visit interaction, as well as the continuous, fixed covariates of baseline value.
 
Analysis of Key Secondary endpoint variables:
 
Key secondary efficacy endpoint variables will be analysed with the same MMRM model as the primary efficacy endpoint.
 
Analysis of Secondary endpoint variables:
 
Continuous secondary diabetes status variables will be compared using the same MMRM model as for the primary efficacy endpoint.
		

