6.4.3 Exploratory Endpoints

All data collected at the 24-month follow-up visit (Visit 8) will be regarded as exploratory endpoints and will be presented using summary statistics including data from the main study period where only the patients that participated in the Extended Study Period will be included. The following statistical analyses will be repeated for the whole study period:

- The change in log-transformed C-peptide $AUC_{\text{mean } 0-120 \text{ min}}$ during an MMTT from baseline to Month 24

- Change in HbA1c between baseline and 24 months
- Change in daily exogenous insulin consumption between baseline and 24 months
- Change in Fasting C-peptide between baseline and 24 months.
- Change in glycemic variability/fluctuations (evaluated from data from continuous glucose monitoring FreeStyle LibrePro, FGM) over 14 day period between Screening and 24 months.
- Rate of hypoglycemic events using Poisson regression including randomization strata (GAD65A)
- Number of patients having at least 1 severe hypoglycemic event using Cochran/Mantel-Haenszel Test stratified for randomization strata (GAD65A)
- Change in body weight and body mass index (BMI) between baseline and 24 months

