7 TRIAL DESIGN

7.1 Description of the Study Design and Procedures

The study is a 2-arm, randomized, double-blind, placebo-controlled study in GAD65A positive T1D patients aged ≥ 12 and < 25 years old, diagnosed within 6 months prior to screening with fasting C-peptide levels ≥ 0.12 nmol/L (0.36 ng/ml). In total, the aim is to recruit 106 patients at approximately 22 sites. The patients will be followed for 15 months with 7 visits to the clinic (Table 2) in the Main Study Period. All patients that are ongoing, i.e. have not performed Visit 7 (Month 15) when protocol version 7 is approved and implemented, will be asked to participate in the Extension Study Period which include Visit 8 at month 24 (Table 3).

Patients and parent(s)/guardian(s), as applicable, will provide written informed consent before any study-related procedures are performed. On Day 1 (Visit 2), 2-4 weeks after the Screening Visit, patients eligible for the study will be randomized in a 1:1 ratio stratified by GAD65A level and country to receive either:

- i) three (3) intralymphatic injections with 4 μ g Diamyd on Days 30, 60, and 90 and; ii) oral vitamin D 2000 IE daily for 4 months (from Day 1 through Day 120)
- i) three (3) intralymphatic injections of Placebo for Diamyd on Days 30, 60, and 90 and; ii) oral Placebo for vitamin D daily for 4 months (from Day 1 through Day 120)

The treatment schedule is given in Table 1.

At the screening visit patients will be assigned a 3-digit country/site number and a 3-digit sequential screening number and these numbers together will be used as a 6-digit patient identification (Patient Number), i.e. XXX-YYY.

Individual patients will be exposed to Diamyd for a maximum of 3 months and vitamin D for a maximum of 4 months. All patients will continue to receive intensive insulin treatment from their personal physicians during the whole study period. All patients will be monitored for at least 1 hour after administration of each Diamyd/placebo injection.

When the last patient has completed the double-blind study period, the study code will be broken and results analyzed.

Table 1 Schedule of Patient Visits for DIAGNODE-2

	Main Study Period							Extension Study Period
	Screening	Intervention and Follow-up						Follow-up
	Day -14 to -28 Screening	Day 1 Baseline	Day 30 Month 1 ±5 days	Day 60 Month 2 ±5 days	Day 90 Month 3 ±5 days	Day 180 Month 6 ±14 days	Day 450 Month 15 ±14 days	Day 720** Month 24 ±14 days

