10.1.1 Method of Assigning Patients to Treatment Groups

A computer-generated randomization list will be produced by the IWRS system. After confirmation of eligibility at Visit 2 patients will be randomized in a 1:1 ratio (Arm 1:Arm 2) across all study sites. Randomization will be stratified by country and GAD65A level to ensure that an equal number of patients in respective age group are included in each arm.

- Arm 1: Diamyd + vitamin D
- Arm 2: Placebo for Diamyd + Placebo for vitamin D

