13.2.3.2.2 Other Secondary Variables of Diabetes Status

Summary statistics (including Student's t based 95% CIs and p-value for the difference between Diamyd and Placebo) for change in glycemic variability/fluctuations (evaluated from data from continuous glucose monitoring FreeStyle LibrePro, FGM) over 14-day period between Screening and 15 months. Further analysis of the data from the 14-day FreeStyle LibrePro, periods will be presented in the SAP.

The following secondary efficacy endpoint variables will be analyzed with the same model as the primary efficacy endpoint (details on log-transformations will be given in the SAP):

- Proportion of patients with by IDAA1c ≤ 9 at 15 months.
- Change in Fasting C-peptide between baseline and 15 months.
- Change in C-peptide measured at 30, 60, 90, and 120 minutes during MMTT at 15 months.
- Change in maximum C-peptide during MMTT between baseline and 15 months.

The following secondary efficacy endpoints will be presented using summary statistics and p-value from Cochran/Mantel-Haenszel Test stratified for randomization strata (GAD65A level) will be given along with 95% CIs calculated according to the Clopper-Pearson method:

- Proportion of patients with a stimulated maximum C-peptide level above 0.2 nmol/L (0.6 ng/ml) at 15 months.
- Proportion of patients with a stimulated 90min C-peptide level above 0.2 nmol/L (0.6 ng/ml) at 15 months.
- Number of patients having at least 1 severe hypoglycemic event using Cochran/Mantel-Haenszel Test stratified for randomization strata (GAD65A level).
- Change in body weight and BMI between baseline and 15 months

In addition, the number of self-reported episodes of severe Hypoglycaemia (severe Hypoglycaemia defined as needing help from others and/or seizures and/or unconscious) between baseline and 15 months will be assessed using Poisson regression including randomization strata (GAD65A level) where rate ratios with 95% CI and p-value will be given.

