13.2.3.3 Analysis of Exploratory Endpoint Variables

All data collected at the 24-month follow-up visit (Visit 8) will be regarded as exploratory endpoints and will be presented using summary statistics including data from the Main Study Period where only the patients that participated in the Extension Study Period will be included. The following statistical analyses will be repeated for the whole study period:

- The change in log-transformed C-peptide $AUC_{\text{mean } 0-120 \text{ min}}$ during an MMTT from baseline to Month 24
- Change in HbA1c between baseline and 24 months
- Change in daily exogenous insulin consumption between baseline and 24 months
- Change in Fasting C-peptide between baseline and 24 months.

- Change in glycemic variability/fluctuations (evaluated from data from continuous glucose monitoring FreeStyle LibrePro, FGM) over 14 day period between Screening and 24 months.
- Rate of hypoglycemic events using Poisson regression including randomization strata (GAD65A level)
- Number of patients having at least 1 severe hypoglycemic event using Cochran/Mantel-Haenszel Test stratified for randomization strata (GAD65A level)
- Change in body weight and BMI between baseline and 24 months

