13.2.5 Adjustment for Covariates

Change from baseline analyses will be adjusted for baseline and all other analyses will be adjusted for randomization strata (GAD65A level).

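### Randomisation is stratified by country and GAD65A level, but the analyses adjust for GAD65A level only, without a stated reason

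*Protocol*

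**What the plan says.** **Randomisation.** Section 7.1 has patients "randomized in a 1:1 ratio stratified by GAD65A level and country". Section 10.1.1 names the same two factors but attaches a different purpose, balance between the arms by age: "Randomization will be stratified by country and GAD65A level to ensure that an equal number of patients in respective age group". Age is not a stratification factor, and no age groups are defined.

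**Analysis.** The synopsis gives the primary MMRM "fixed, categorical effects of treatment, randomization strata (GAD65A level), visit and treatment by visit interaction" plus baseline. Section 13.2.3.1 has the same single factor in its bracket: "strata (GAD65A level), visit and treatment by visit interaction". The completers ANCOVA in 13.2.3.1 also has GAD65A level as its only stratum. The key secondary endpoints inherit the primary model (13.2.3.2.1). In 13.2.3.2.2 the Cochran/Mantel-Haenszel tests use GAD65A level alone, as does the "Poisson regression including randomization strata (GAD65A level) where rate ratios". The 24-month analyses follow suit: "Rate of hypoglycemic events using Poisson regression including randomization strata (GAD65A" in 6.4.3 and "Rate of hypoglycemic events using Poisson regression including randomization strata (GAD65A level" in 13.2.3.3.

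**General rule.** Section 13.2.5 reads: "Change from baseline analyses will be adjusted for baseline and all other analyses will be adjusted for randomization strata (GAD65A level".

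**Nearest thing to a reason.** Section 13.2.7 explains only why results will not be displayed by centre. It does not discuss country as a stratum or a model term. Section 13.2 says the SAP will follow the protocol's outline, so this model carries forward.

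**The concern.** A factor used to restrict the randomisation normally belongs in the primary model. Stratifying by country removes chance country imbalance from the real variability of the treatment estimate. If the model then omits country, the between-country variance stays in the residual, and the reported standard error exceeds the true one. At stake is precision in the primary and key secondary comparisons, not a false positive.

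There is also a clarity problem. The bracket after the strata term misstates the trial's own design. Section 13.2.5, read literally, gives change-from-baseline analyses a baseline adjustment and no strata, which contradicts 13.2.3.1.

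**Working it through.** **1. The plan's own sample size.** Section 13.1 gives two-sided 0.05, 90% power, SD 0.20 and 0.134 on the transformed scale. Taking 0.134 as the between-arm difference:

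n per arm = 2(1.960 + 1.282)² × 0.20² / 0.134² = 46.8, so 47.

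47 / 0.9 = 52.2, so 53 per arm and 106 in total, as stated. An exact t-test needs 48 per arm (power 90.1%), and 96 / 0.9 = 106.7. The sample size does not depend on the country question. The standardised effect is 0.134 / 0.20 = 0.67, with about 96 patients evaluable.

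**2. Closed form under perfect balance.** Let R² be country's share of residual variance. Without country, the interval is wider by the factor 1/√(1 − R²), and type I error is 2[1 − Φ(1.96/√(1 − R²))]. For R² of 0/2/5/10/20%, the factors are 1.00/1.01/1.03/1.05/1.12 and the errors 5.0/4.8/4.4/3.9/2.8%.

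**3. Simulation of the two-visit MMRM.** From the protocol: 106 patients, four countries, MMTT visits at Months 6 and 15, unstructured covariance, treatment by visit, GAD65A term. Assumed, because the protocol does not give them: R², country shares of 45/25/15/15%, blocks of 4, two GAD65A levels, visit correlation 0.7, and 10 patients lost at random. Outcomes are on the baseline-adjusted residual scale. There were 4,000 trials per scenario (95% Monte Carlo error about 0.7 points for type I error and 0.9 for power). The country effect is the same at both visits.

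| R² | Model SE without / with country | Interval wider without | Type I error without | Power without / with |
|---|---|---|---|---|
| 0% | 0.203 / 0.204 | about 0% | 5.1% | 90.2 / 90.0% |
| 2% | 0.204 / 0.202 | about 1% | 4.9% | 90.6 / 90.7% |
| 5% | 0.204 / 0.199 | about 2% | 4.6% | 90.0 / 90.8% |
| 10% | 0.204 / 0.194 | about 5% | 4.0% | 90.9 / 92.4% |
| 20% | 0.204 / 0.183 | about 12% | 3.4% | 91.8 / 95.0% |

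With country in the model, type I error is about 5% throughout. At 20%, the SE without country is 0.204 against a true SD of 0.186 for the same estimator: 0.204 / 0.186 = 1.10, about 10% too large.

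**4. Country effect at Month 15 only.** A country main effect then recovers less. Intervals without it are 0/0.5/1.6/3.7/8.1% wider. Power without/with is 89.9/89.8, 90.2/90.4, 90.6/90.9, 90.0/91.8 and 92.2/94.2%.

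**5. Cross-check.** A separate single-visit simulation (5,000 runs, country shares 40/30/20/10%) at R² of 0/5/10/20% gives type I error without country of 5.3/4.6/3.9/2.6%, and power of 89.5/90.7/91.3/92.3% without against 89.4/91.5/93.0/95.3% with. At 10%, the estimate's true SD is the same either way (0.0388 and 0.0387), but the model SE is 0.0407 without country and 0.0387 with it.

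**6. Sparse events.** With the step 3 country shares and 20,000 draws of 106 patients, if 3/5/10% have a severe hypoglycaemic event (assumed), on average 5.5/4.3/2.5 of the 8 country-by-GAD65A cells contain no event.

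**The case against.** The strongest reply is that little is lost. The error is conservative. Simulated power without country stays at about 90% or above, and the gains from adding it are -0.2, 0.1, 0.8, 1.5 and 3.2 points, the first three within Monte Carlo error. The larger figures need a strong country effect: on the protocol's SD, a 20% share means a between-country SD of √0.2 × 0.20 = 0.089, two thirds of the 0.134 used for sizing and remaining after baseline adjustment. Nothing in the documents supports an effect of that size. The model is also stated consistently in the synopsis and 13.2.3.1, so it is clear what will be fitted, and a country-adjusted sensitivity analysis could sit in the SAP.

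Most of this stands as to size: the 0 to 5% rows are the safer guide. It does not remove the point. The protocol itself fixes the terms of the primary model and leaves only further sensitivity analyses to the SAP. A consistent omission is still unexplained, and the label for the strata is wrong. For the count and proportion endpoints, the objection has more force: sparse data are a fair reason to keep GAD65A alone, and only that reason is missing.

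**Conclusion.** The concern holds. The primary and key secondary models omit one of the two randomisation factors without explanation. The consequence is modest: no inflation of type I error, no loss of the planned power, and nothing material if country is not prognostic. Under the assumed 0 to 20% range, a small and nearly free gain in precision is forgone. The exact levels vary with the assumptions (at 20%, type I error is 3.4% in the MMRM simulation, 2.8% in closed form and 2.6% in the cross-check), but the direction does not. The figures are for the primary endpoint; the key secondary endpoints were not simulated. The 13.2.5 sentence and the age-group clause are drafting errors, and the age clause has no bearing on the test. The change should be made, though the trial's validity does not hang on it.

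**What to change.** 1. Define the randomisation strata throughout as country and GAD65A level. Add country as a fixed categorical effect to the primary and key secondary MMRM and to the completers ANCOVA, or state why it is left out.
2. Reword 13.2.5 so that change-from-baseline analyses adjust for baseline and the randomisation strata, in line with 13.2.3.1.
3. For the Cochran/Mantel-Haenszel and Poisson analyses, either keep GAD65A alone and give sparse data as the reason, or include country with a pooling rule for small countries fixed before unblinding.
4. Delete or correct the age-group clause in 10.1.1. No age covariate is needed on this account.

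The cost is wording in the synopsis, 10.1.1, 13.2.3.1, 13.2.3.2 and 13.2.5, with the strata label aligned in 6.4.3 and 13.2.3.3. The continuous-endpoint models give up 3 of about 93 degrees of freedom, a simulated power cost of about 0.2 points if country has no effect. The sample size stays at 106 and no new data are needed.

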13 STATISTICAL METHODS

13.1 Estimation of Sample Size

A total sample size of 106 patients is planned for a 1:1 randomization in order to provide 90% power to detect a 50% difference in geometric mean C-peptide ($AUC_{\text{mean } 0-120 \text{ min}}$) during an MMTT at 15 months between the active arm and placebo arm using a two-sided test at the 0.05 significance level. The sample size has been adjusted to allow for 10% loss to follow-up. This is based upon a t-test employing $\ln(X+1)$ normalizing transformation of C-peptide ($AUC_{\text{mean } 0-120 \text{ min}}$) during an MMTT at 15 months and assumed mean and standard deviation estimates, on the transformed scale, of 0.134 and 0.20, respectively¹

It is estimated that there will be a screening failure rate of 16%. To ensure that 106 patients are screened and enrolled approximately 127 patients will be screened.

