13.2.3.2 Analysis of Secondary Endpoint Variables

13.2.3.2.1 Key Secondary Variables of Diabetes Status

The following key secondary efficacy endpoint variables will be analysed with the same model (MMRM) as the primary efficacy endpoint:

- Change in IDAA1c between baseline and 15 months.
- Change in HbA1c between baseline and 15 months.
- Change in daily exogenous insulin consumption between baseline and 15 months.

The analysis of key secondary endpoints will be subject to the same sensitivity analyses as the primary efficacy analysis. However, exploration of key secondary endpoints by covariate and subgroups analyses will be based on the observed results for respective endpoint.

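### The MMRM gives baseline one slope for all visits, which can cost precision at Month 15, mainly for the five-visit key secondary endpoints

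*Protocol*

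**What the plan says.** Protocol 13.2.3.1 names the fixed effects of the primary model: treatment, GAD65A stratum, "visit and treatment by visit interaction, as well as the continuous, fixed covariates of log-transformed baseline C-peptide". The Synopsis repeats the list. The covariance is free: "An unstructured (co)variance structure will be used to model the within-patient errors". The primary comparison is the treatment contrast at Month 15.

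Section 13.2.3.2.1 extends this: "The following key secondary efficacy endpoint variables will be analysed with the same model (MMRM) as the primary efficacy endpoint". The endpoints are IDAA1c, HbA1c and daily insulin dose. Section 13.2.3.2.2 also applies the primary model to several further C-peptide measures.

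Table 2 schedules the post-baseline MMTT at Months 6 and 15 only. HbA1c and insulin dose are collected at Months 1, 2, 3, 6 and 15, so IDAA1c, which combines them, also has five post-baseline visits. The protocol does not say which of these visits enter the key secondary models.

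**The concern.** A single baseline coefficient assumes that baseline predicts every later visit equally well. In recent-onset disease followed from Month 1 to Month 15, that relation may well fade. The fitted slope is then a weighted average that favours visits with small residual variance, which are the early ones. Applied at Month 15 it is too steep, and baseline variation that a visit-specific slope would remove stays in the contrast.

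The key secondary endpoints are more exposed than the primary. Four of their five scheduled visits fall in the first six months. They are tested in a fixed sequence (13.2.4), so precision lost at IDAA1c can block HbA1c and insulin dose. Section 13.1 sizes the trial on C-peptide alone, so no power is stated for them.

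**Working it through.** **1. The plan's own sample size.** Inputs from 13.1: "A total sample size of 106 patients is planned for a 1:1 randomization"; "provide 90% power to detect a 50% difference in geometric mean C-peptide"; "using a two-sided test at the 0.05 significance level"; "standard deviation estimates, on the transformed scale, of 0.134 and 0.20, respectively"; "The sample size has been adjusted to allow for 10% loss to follow-up". Taking 0.134 as the between-arm difference and 0.20 as the SD, the normal formula gives 2 × (1.960 + 1.282)² × 0.20² / 0.134² = 46.8, or 47 per arm. The t-test needs 48 per arm (power 90.1%), 96 in total, and 96/0.9 = 106.7. The planned 106 is reproduced. It rests on a t-test without baseline adjustment.

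**2. Formulas.** Take complete data and an unstructured covariance. Let b be the vector of visit-specific slopes on baseline x, and E the residual covariance of the visits given x.
- Common slope: b_c = (1′E⁻¹b) / (1′E⁻¹1).
- Month 15 variance, common slope over visit-specific slope: 1 + (b15 − b_c)² var(x) / e15, where e15 is the Month 15 residual variance.
- Month 15 value with no baseline term, over visit-specific slope: var(y15) / e15.

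Modelling change instead of the value lowers every slope by 1 and leaves these ratios unchanged. All SDs are set to 1, so slopes equal correlations. **The correlations are assumptions; the protocol gives none.**

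**3. C-peptide AUC (Months 6 and 15).** Worked case: baseline correlations 0.8 and 0.6, between-visit correlation 0.7.
- e6 = 1 − 0.64 = 0.36; e15 = 1 − 0.36 = 0.64; residual covariance = 0.70 − 0.48 = 0.22.
- Weight on Month 6 = (0.64 − 0.22) / (0.36 + 0.64 − 0.44) = 0.75.
- b_c = 0.75 × 0.8 + 0.25 × 0.6 = 0.75, against 0.60 at Month 15.
- Ratio = 1 + 0.15² / 0.64 = 1.035.

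Power below is for a difference of 0.134 with 48 per arm and SD 0.20 × √e15, or 0.20 × √(e15 × ratio). Between-visit correlation is 0.7 throughout.

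| Baseline correlation, Month 6 / Month 15 | b_c | Variance ratio | Power, visit-specific → common slope |
|---|---|---|---|
| 0.80 / 0.70 | 0.76 | 1.01 | 99.5% → 99.5% |
| 0.80 / 0.60 | 0.75 | 1.035 | 98.2% → 97.9% |
| 0.85 / 0.60 | 0.81 | 1.07 | 98.2% → 97.5% |
| 0.80 / 0.50 | 0.76 | 1.09 | 96.3% → 94.8% |
| 0.85 / 0.50 | 0.85 | 1.16 | 96.3% → 93.6% |
| 0.90 / 0.50 (extreme) | 0.95 | 1.28 | 96.3% → 91.3% |

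**4. Five-visit endpoints (Months 1, 2, 3, 6, 15).** The correlation between two visits m months apart follows the pattern shown.

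| Pattern | Slope at Months 1, 2, 3, 6, 15 | b_c | Ratio, five visits | Ratio, no baseline term | Ratio, Months 6 and 15 only |
|---|---|---|---|---|---|
| 0.3 + 0.6 × 0.95^m | 0.87, 0.84, 0.81, 0.74, 0.58 | 0.82 | 1.08 | 1.50 | 1.02 |
| 0.2 + 0.7 × 0.9^m | 0.83, 0.77, 0.71, 0.57, 0.34 | 0.71 | 1.15 | 1.13 | 1.02 |
| 0.9^m | 0.90, 0.81, 0.73, 0.53, 0.21 | 0.79 | 1.36 | 1.04 | 1.04 |
| constant 0.5 | 0.50 throughout | 0.50 | 1.00 | 1.33 | 1.00 |

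Third row: e15 = 1 − 0.206² = 0.958, and 1 + (0.206 − 0.794)² / 0.958 = 1.36. In the second and third rows the shared slope is less precise than leaving baseline out.

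**5. Simulation.** With 48 per arm and 4,000 replicates of complete data, the ratios were 1.02 to 1.09 for four two-visit cases, 1.16 for 0.2 + 0.7 × 0.9^m and 1.37 for 0.9^m. Type I error of the common-slope test was 4.5-5.4%, and no bias appeared.

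**The case against.** **Nothing here is invalid.** This stands. Randomisation protects the contrast, and the simulation shows neither bias nor type I error inflation. A reader might infer that a wrong slope at Month 15 makes the primary result unreliable; the calculations do not support that.

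**The primary endpoint hardly suffers.** This also stands. The sample size takes no credit for baseline adjustment, so the common slope uses up part of a bonus.

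**The SAP could add the term.** Section 13.2 leaves details to the SAP, which must follow the protocol's outline. But the protocol lists the fixed effects one by one, so a single slope is a stated choice.

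**The five-visit figure is an inference.** Fair. Use of all scheduled visits is the natural reading but is not stated; with Months 6 and 15 only, the loss is about 2-4% for the decaying patterns shown.

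**The Month 15 ANCOVA fits its own slope.** True, and 13.2.3.2.1 applies the same sensitivity analyses to the key secondary endpoints. It would expose the effect, but it is a sensitivity analysis on completers and does not replace the MMRM.

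**Two stronger readings.** Section 13.2.6 relies on the MMRM for dropouts, so a reader might infer that the single slope also undermines the missing-data handling. Every calculation here assumes complete data, and nothing in the protocol sizes such an effect, so that is not claimed. Much larger variance losses can also be produced by choosing the between-visit correlation freely. For example, 0.9 / 0.5 with 0.8 between visits gives +59%, but that correlation matrix is nearly singular: 1 + 2(0.9)(0.5)(0.8) − 0.81 − 0.25 − 0.64 = 0.02. The protocol gives no basis for such a case.

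**Conclusion.** The point holds as a minor loss of efficiency. For C-peptide AUC the Month 15 variance rises by roughly 1-16% over the assumed correlations. Most cases lose about 0-2 power points, the steepest non-extreme one 2.7 (96.3% to 93.6%), and all tabulated cases stay above 90%. For IDAA1c, HbA1c and insulin dose the rise is roughly 8-36% if all five visits enter the model, and there the covariate can do worse than no adjustment.

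These sizes rest on assumed correlations, equal SDs, complete data and, for the key secondary endpoints, use of every scheduled visit. The direction needs only that the relation to baseline weakens with time. If it does not, the loss is zero.

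**What to change.** Add a baseline-by-visit interaction to the MMRM in 13.2.3.1 and the Synopsis, and state that it applies to the key secondary endpoints and to the other continuous endpoints analysed with the primary model. Also state which post-baseline visits enter each model.

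The cost is one extra parameter for C-peptide AUC (two visits) and up to four for the five-visit endpoints, with about 95 evaluable patients (106 × 0.9 = 95.4). No new data, visits or patients are needed. The change should be fixed before unblinding.
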